6. CLINICAL STUDY POPULATION

6.1. Inclusion Criteria

Subjects must meet all of the following inclusion criteria to be eligible for participation in this study:

1. Subject must be able and willing to comply with the CSP requirements and must sign and date the ICF as approved by the Independent Ethics Committee (IEC) / Institutional Review Board (IRB), prior to any screening evaluations.
2. Subjects must be ≥ 18 and < 65 years of age, on the date of signing the ICF.
3. Documented diagnosis of UC of ≥ 3 months. The criteria for documentation of UC diagnosis based on endoscopy will be medical record documentation, and/or a colonoscopy report dated ≥ 3 months before screening, which shows features consistent with UC.
4. Treatment-experienced subjects with moderately to severely active disease, who have either previously demonstrated inadequate clinical response, loss of response, or intolerance to at least 1 course of standard-of-care (SoC) therapy for UC (i.e., steroids [oral or parenteral, including but not limited to prednisone, prednisolone, budesonide], 5-aminosalicylate [5-ASA] derivatives [including but not limited to mesalamine, sulfasalazine], anti-metabolites [including but not limited to azathioprine, 6 mercaptopurine, methotrexate], anti-TNF agents, anti-integrins, Janus kinase [JAK] inhibitors), as confirmed by the investigator.
5. Moderately to severely active UC as determined at screening by:
 - a. Centrally-read endoscopic evidence of disease activity (MCS-ES ≥ 2 OR UCEIS ≥ 4) with a minimum disease extent of 15 cm from anal verge; AND
 - b. MCS SF subscore ≥ 1 ; AND
 - c. MCS RB subscore ≥ 1 .
6. Subject must be otherwise healthy on the basis of physical examination, medical history, vital signs, 12-lead electrocardiogram (ECG), and clinical laboratory tests performed during

screening. If there are abnormalities, they should be consistent with the underlying illness in the study population or considered not to be clinically significant in the opinion of the investigator.

7. Female subject of child bearing potential must have a negative highly sensitive (serum beta human chorionic gonadotropin) pregnancy test at screening and a negative pregnancy test prior to the first dose of IP.
8. Female subject of child bearing potential or male subject must agree to use highly effective contraception/preventive exposure measures (as described in Section 6.3.1).
9. Female subjects of nonchildbearing potential (as defined in Section 6.3.1) must also have a negative blood pregnancy test at screening. For surgical sterilization, documented confirmation will be requested.
10. Subject must have a body mass index (BMI) between 17-30 kg/m², inclusive.
11. Subject must be able and willing to comply with restrictions on prior and concomitant medication (as described in Section 6.3.2).
12. Subjects currently receiving the following standard of care therapies for UC are eligible providing they have been on a stable dose for the designated period of time and are anticipated to be stable throughout the study:
 - a. oral corticosteroids (prednisone \leq 20 mg/day or equivalent (see conversion table in [Appendix 1](#)) or budesonide \leq 3 mg/day) stable dose for at least 2 weeks prior to first IP dosing.
 - b. oral 5-ASA compounds (mesalamine \leq 4 g/day or sulfasalazine \leq 4 g/day) stable dose for at least 4 weeks prior to first IP dosing.
 - c. oral thiopurines (azathioprine \leq 2.5 mg/kg/day and 6-mercaptopurine 1.5 mg/kg/day) stable dose for at least 12 weeks prior to first IP dosing, or methotrexate \leq 20 mg/week, stable dose for at least 12 weeks prior to first IP dosing.
13. The results of the following laboratory tests at screening must be as specified below:
 - a. Hemoglobin International System of Units (SI): \geq 90 g/L
 - b. White blood cells (WBCs) \geq 3.0 x 10⁹ cells/L
 - c. Neutrophils \geq 2.0 x 10⁹ cells/L
 - d. Lymphocytes \geq 1.0 x 10⁹ cells/L
 - e. Platelets \geq 100 x 10⁹ cells/L
 - f. Serum alanine aminotransferase (ALT) and aspartate aminotransferase (AST) \leq 1.5 x upper limit of normal range (ULN)
 - g. Total bilirubin level \leq 1.5 x ULN unless the subject has been diagnosed with Gilbert's disease and this is clearly documented
 - h. Alkaline phosphatase \leq 1.5 x ULN
 - i. Creatinine clearance $>$ 60 mL/min. Creatinine clearance will be calculated using the Cockroft-Gault formula.

6.2. Exclusion Criteria

Subjects meeting one or more of the following criteria cannot be selected for this clinical study:

1. Diagnosis of Crohn's disease, indeterminate colitis, ischemic colitis, fulminant colitis, or toxic megacolon.
2. Prior surgical intervention for UC (e.g. colectomy, partial colectomy, ileostomy or colostomy) or likely requirement for surgery for UC, during the study.
3. History or evidence of incompletely resected colonic mucosal dysplasia.
4. Subject has a known hypersensitivity to IP ingredients or history of a significant allergic reaction to IP ingredients as determined by the investigator, such as anaphylaxis requiring hospitalization.
5. Currently on any chronic systemic (oral or intravenous) anti-infective therapy for chronic infection (such as pneumocystis, cytomegalovirus, herpes zoster, atypical mycobacteria).
6. Active clinically significant infection OR any infection requiring oral or systemic anti-infective therapy within 2 weeks prior to screening (including use of oral anti-infective therapy for UC).
7. History of tuberculosis (TB) diagnosis or evidence of active or latent infection with *Mycobacterium tuberculosis* as defined by one of the following assessments:
 - a. Positive QuantiFERON-TB Gold test result,
OR
 - b. Chest radiograph (posterior anterior view) taken within 12 weeks prior to screening, read by a qualified radiologist or pulmonologist, with evidence of current active TB or old inactive TB.
8. Subject has a known or suspected history of or a current immunosuppressive condition, or a history of invasive opportunistic infections (e.g. human immunodeficiency virus [HIV] infection, histoplasmosis, listeriosis, coccidioidomycosis, pneumocystosis, aspergillosis).
9. Subject has a history of malignancy within the past 5 years prior to screening with the exception of excised and curatively treated non-metastatic basal cell carcinoma or squamous cell carcinoma of the skin or carcinoma in situ of cervix which is considered cured with minimal risk of recurrence.
10. Subject has a history or presence of clinically significant abnormalities detected on 12-lead ECG of either rhythm or conduction e.g. known long QT syndrome or a QT interval corrected for heart rate using Fridericia's formula [QTcF] >450 ms (male), >460 ms (female) detected on the 12-lead ECG. A first-degree atrioventricular block will not be considered as a significant abnormality.

11. Female subject is pregnant or breast feeding or intending to become pregnant or breastfeed during the study.
12. Dependence on parenteral nutrition.
13. History of major surgery (requiring regional block or general anesthesia) within the last 12 weeks prior to screening, including bowel surgery.
14. Investigator or other study staff or relative thereof who is directly involved in the conduct of the study.
15. Subject has any condition or circumstances that, in the opinion of the investigator, may make a subject unlikely or unable to complete the study or comply with study procedures and requirements (e.g., active alcohol or drug abuse).
16. Subject has taken any disallowed therapies before the planned first dose of IP.
17. Subject has any condition (including but not limited to chronic cardiac or pulmonary disease, chronic renal failure) for which, in the opinion of the investigator, participation would not be in the best interest of the subject (e.g., compromise the well-being) or that could prevent, limit, or confound the protocol-specified assessments.
18. Exhibit acute severe UC per the following criteria:
 - a. bloody diarrhea \geq 6/day
AND
 - b. any of the following signs of systemic toxicity:
Body temperature (oral or tympanic) \geq 37.8°C
OR
Resting pulse (after 5 min seated position) $>$ 90 beats per min
OR
hemoglobin $<$ 105 g/L,
OR
erythrocyte sedimentation rate $>$ 30 mm/h
OR
C-reactive protein (CRP) $>$ 30 mg/L.
19. Screening stool sample positive for ova and/or parasites, *Clostridium difficile* toxin, *Escherichia coli*, *Salmonella species* (spp), *Shigella spp*, *Campylobacter spp* or *Yersinia spp*.
20. Subject has a chronic hepatitis B virus (HBV) infection, as defined by persistent HBV surface antigen (HBsAg) positivity. Subject has hepatitis C virus infection, as defined by positive hepatitis C virus (HCV) antibody (Ab) at screening and detectable HCV viremia. Subjects with positive HCV Ab must undergo reflex HCV RNA testing, and subjects with HCV RNA positivity will be excluded. Subjects with positive HCV Ab and negative HCV RNA are eligible.

21. Subject testing positive at screening for SARS-CoV-2 infection as detected by real time polymerase chain reaction (RT-PCR), subjects presenting any signs or symptoms as detected at baseline following careful physical examination (e.g. cough, fever, headaches, fatigue, dyspnea, myalgia, anosmia, dysgeusia, anorexia, sore throat, others) or reporting any signs and symptoms for the 2 preceding weeks, or subjects who have been exposed to individuals with confirmed or suspected diagnosis of SARS-CoV-2 within 2 weeks prior to baseline (BMJ, 2020). In addition, any other locally applicable standard diagnostic criteria may also apply to rule out SARS-CoV-2 infection.
22. Subject has presence or sequelae of gastrointestinal, liver, kidney (creatinine clearance ≤ 90 mL/minute, for elderly ≤ 60 mL/minute, using the Cockcroft-Gault formula: if calculated result is ≤ 90 mL/minute, for elderly ≤ 60 mL/minute, if applicable, a 24-hour urine collection can be done) or other conditions known to interfere with the absorption, distribution, metabolism, or excretion of drugs.
23. Subject concurrently participates or participated in a drug, drug/device or biologic investigational research study within 12 weeks or 5 half-lives of the IP, whichever is longer, prior to the first dose.

6.3. Prohibition and Restrictions

6.3.1. Precautions for Sexual Intercourse

Highly effective contraceptive measures for both males and females of childbearing potential must be documented in the source documents.

6.3.1.1. Female Subjects

Female subjects are considered of non-childbearing potential if they meet one of the following criteria:

- No menses for 12 or more months without an alternative medical cause. A high follicle stimulating hormone (FSH) level in the post-menopausal range may be used to confirm a post-menopausal state in women not using hormonal contraception or hormonal replacement therapy. However in the absence of 12 months of amenorrhea, a single FSH measurement is insufficient.
- Permanently surgically sterile (bilateral oophorectomy, i.e., surgical removal of ovaries, bilateral salpingectomy or hysterectomy, i.e., surgical removal of uterus).

All other female subjects are considered to be of childbearing potential (WOCBP) and must use one of the following highly effective methods of birth control prior to the first dose of IP, during the clinical study and for at least 35 days after the last dose of IP:

- Combined (estrogen and progesterone containing) (oral, intravaginal, transdermal) hormonal contraception associated with inhibition of ovulation plus a barrier method.
- Progesterone-only hormonal (oral, injectable, implantable) contraception associated with inhibition of ovulation plus a barrier method.

- Intrauterine device.
- Intrauterine hormone-releasing system plus a barrier method.
- Bilateral tubal occlusion.
- Sexual abstinence defined as refraining from heterosexual intercourse during the entire period of risk associated with the study treatments. The reliability of sexual abstinence needs to be evaluated in relation to the duration of the clinical study and the preferred and usual lifestyle of the subject.

Periodic abstinence (e.g., calendar, symptothermal, post-ovulation methods), declaration of abstinence for the duration of a clinical study, withdrawal, spermicides only, and lactational amenorrhea method are not acceptable as methods of contraception.

In case a WOCBP has a vasectomized partner, provided that partner is the sole sexual partner of the WOCBP clinical study participant and that the vasectomized partner has received medical assessment of the surgical success, then she is not required to use an additional form of contraception.

Within these limits, the specific forms of contraception employed are left to the discretion of the subject, the investigator, and/or the subject's physician.

The safety of GLPG3970 during breastfeeding is unknown. Nursing women are not allowed to take part in this clinical study.

6.3.1.2. Male Subjects

Non-vasectomized male subjects with female partners of childbearing potential must be willing to use a condom from the time of the first dose of IP, during the clinical study, and for at least 7 days after the last dose of IP, in addition to having their female partner use one of the following forms of contraception:

- Intrauterine device.
- Intrauterine hormone-releasing system.
- Combined (estrogen and progesterone containing) hormonal contraception associated with inhibition of ovulation (oral, intravaginal, transdermal).
- Progesterone-only hormonal contraception associated with inhibition of ovulation (oral, injectable, implantable).

Sexual abstinence defined as refraining from heterosexual intercourse is considered a highly effective contraceptive measure only if it is the preferred and usual lifestyle of the subject. The reliability of sexual abstinence needs to be evaluated in relation to the duration of the clinical study.

Periodic abstinence (e.g. calendar, symptothermal, post-ovulation methods), declaration of abstinence for the duration of a clinical study, withdrawal, spermicides only, and lactational amenorrhea method are not acceptable methods of contraception.

In a case where the female partner of a male subject, provided that this partner is the sole sexual partner of the subject, has undergone documented surgical sterilization that was performed more than 1 year before screening, then the subject is not required to use an additional form of contraception.

Vasectomized male subjects with female partners of childbearing potential are not required to use an additional form of contraception providing that surgical sterilization has been successful (documented azoospermia by semen analysis).

No sperm donation is allowed from the first dose of IP during the clinical study until 7 days after the last dose of IP.

6.3.2. Prior and Concomitant Medications

Prior and concomitant therapies taken for long-term treatment of pre-existing conditions are allowed, provided they are in accordance with the inclusion and exclusion criteria (see Sections [6.1](#) and [6.2](#), respectively) and with the prohibitions and restrictions listed below.

All medications used for UC within 2 years prior to screening should be recorded with approximate dates of use (year, duration in months). In case of multiple courses of steroids, only the most recent course needs to be recorded. Information on previous failed courses of UC therapy should be reported, indicating the class/product(s).

In case additional concomitant medications need to be administered or dose adjustments for pre-existing conditions (except for UC) are needed during the study, the risk/benefit to the subject should be carefully assessed by the study physician and consideration given to the timing of any necessary introduction of new medications.

If during the study, the subject's condition necessitates the use of prohibited medication, the use of IP may be interrupted, preferably after consultation with the sponsor's medical leader. Re-introduction of IP can be considered after the treatment course with the prohibited medication has been stopped and after consultation with the sponsor's medical leader.

During the study, subjects will be instructed to record any change in concomitant medication in a diary (see Section [8.8.1](#)).

Permitted Medications:

All other medications are permitted as long as they are not listed in the section on prohibited/restricted medications below.

Prohibited/Restricted Medications:

The following rules should apply:

| Medication | Restriction |
|---|--|
| Antibiotics/ anti-infectives | Oral antibiotics/ anti-infectives: not allowed within 2 weeks prior to screening. Intravenous antibiotics/ anti-infectives: not allowed within 8 weeks prior to screening. During the study: not allowed for the treatment of bowel related infections up to the follow-up visit (allowed for treatment of other infections). Allowed for the treatment of infections (other than bowel related infections). |
| Corticosteroids (intramuscular or intravenous) | Not allowed within 4 weeks prior to screening and up to the follow-up visit. |
| Corticosteroids (oral) ² | Oral corticosteroids (prednisone \leq 20 mg/day or equivalent (see conversion table in Appendix 1) or budesonide \leq 3 mg/day) allowed at stable dose for at least 2 weeks prior to first IP dosing. (see inclusion criterion 12) |
| Oral 5-ASA compounds | Mesalamine \leq 4 g/day or sulfasalazine \leq 4 g/day allowed at stable dose for at least 4 weeks prior to first IP dosing. Please also refer to the dosing instructions for sulfasalazine below under 'further guidance for the use of concomitant medications'. |
| Rectal formulation therapies (5-ASA compounds or corticosteroids) | Not allowed within 2 weeks prior to screening endoscopy and up to the last IP dose. |
| Oral thiopurines and methotrexate | Azathioprine \leq 2.5 mg/kg/day and 6-mercaptopurine 1.5 mg/kg/day, allowed at stable dose for at least 12 weeks prior to first IMP dosing. Methotrexate \leq 20 mg/week, allowed at stable dose for at least 12 weeks prior to first IP dosing. |
| Lymphocyte depleting therapies (including, but not limited to, alemtuzumab, cyclophosphamide, tacrolimus, cyclosporine, leukocyte apheresis, total lymphoid radiation or rituximab) | Rituximab is not allowed 6 months prior to screening and up to the follow-up visit. Cyclophosphamide and lymphocyte apheresis are not allowed 3 months prior to screening and up to the follow-up visit. Cyclosporine and tacrolimus are not allowed 30 days prior to screening and up to the follow-up visit. Alemtuzumab treatment and total lymphocyte radiation are not prior to the study or at any time during the study up to follow-up. |
| Anti-TNF Anti-integrin monoclonal antibodies Tofacitinib | Not allowed during screening period and for 5 half-lives prior to first MP dosing and up until the follow up visit. |
| Vaccines ^a | Live or attenuated vaccines not allowed within 60 days prior screening. Live or attenuated vaccines: not allowed throughout the study and up to the follow-up visit Inactivated vaccines should be administered according to local vaccination standards whenever medically appropriate. |

^a Refer to [Appendix 2](#) for further vaccination-related recommendations

Other prohibited medications and dietary/herbal products:

The following medications should be discontinued at least 2 weeks or 5 half-lives of the drug, whichever is longer, prior to the first dose of IP administration and throughout the study:

A 4x4 grid of black and white blocks. The top-left block is black. The top-right block is white. The bottom-left block is black. The bottom-right block is white. The other four blocks are black. The grid is composed of 16 smaller squares.

Additional guidance for the use of concomitant medications:

This figure displays a 2D grayscale heatmap. The central feature is a dark gray, elongated shape, approximately 10 pixels wide and 100 pixels long. It is centered on a white background. The background is filled with numerous small black noise pixels. The feature's ends are slightly irregular, with some white pixels visible at the very tips.

— [REDACTED]

■ [REDACTED]

■ [REDACTED]

■ [REDACTED]

■ [REDACTED]

The list provided in [Appendix 3](#) through [Appendix 8](#) are non-exhaustive.

In case of questions on concomitant medications, the sponsor's medical monitor (as per study contact list) and sponsor's medical leader can be contacted.

6.3.3. Food and Beverage Restrictions

Subjects must come for the study visits, during the treatment and FU period, in the morning. At baseline (Visit 1), Day 15 (Visit 3), and Day 43 (Visit 5) and if applicable the ED visit, subjects need to come for the study visits in a fasting state (no food intake for at least 8 hours).

Subjects will refrain from the consumption of grapefruit juice, grapefruit or Seville oranges beginning 48 hours prior to administration of the initial dose of IP, throughout the study until 7 days after the last IP administration.

6.4. Treatment Discontinuation (Temporarily and Permanently), Subject Withdrawal and Study Termination

A subject may be withdrawn from the clinical study at any time without the subject's consent if the investigator or sponsor determines that it is not in the best interest of the subject to continue participation. In such case, the reason for withdrawal will be documented in the source documents, and the subject will be asked to complete the ED visit and FU visit for safety assessments.

Treatment with IP should be discontinued by the investigator (who may consult the sponsor's medical leader) for any of the following conditions:

- Life-threatening adverse event (AE) or an SAE that places the subject at immediate risk.
- Serious infections deemed related to study treatment by the investigator, and requiring parenteral antimicrobial therapy and/or hospitalization.
- Confirmed pregnancy or lactation.
- Arrhythmia or conduction abnormality, including but not limited to prolonged QTcF, where the severity is categorized as Common Terminology Criteria for Adverse Events (CTCAE) Grade 3 or higher (QTc >500 ms on at least 2 separate ECGs), or clinically significant arrhythmia from any grade.
- Liver enzyme increase (see also [Appendix 9](#))
 - AST and/or ALT ≥ 8 x the ULN.
 - AST and/or ALT elevations ≥ 3 x ULN with signs of liver damage (i.e., with the appearance of fatigue, nausea, vomiting, right upper quadrant pain or tenderness, fever, rash and/or eosinophilia [$>5\%$], and/or total bilirubin ≥ 2.0 x ULN or international normalized ratio [INR] >1.5)
 - In addition, a dose interruption or reduction (if applicable) should be considered if AST and/or ALT ≥ 3 x ULN and <5 x ULN and dosing with IP should be interrupted if AST and/or ALT ≥ 5 and <8 x ULN.
- Subjects presenting with signs and symptoms of SARS-CoV-2 infection should immediately contact the site investigator, who should inform the sponsor's medical responsible as soon as possible, and report an AE/SAE as applicable. In case of suspected SARS-CoV-2 infection RT-PCR and serology tests should be performed to confirm the infection. The investigator, preferably after consultation with the sponsor's medical responsible, must discontinue the subject from the study. The subject could be tested for SARS-CoV-2 in facilities outside the study site and if so, the subject should be instructed to immediately inform the study investigator if the test is positive and test results should be shared with the investigator as soon as possible.

For subjects having:

- AST or ALT ≥ 8 xULN
- AST or ALT ≥ 3 xULN with signs of liver damage (i.e. with the appearance of fatigue, nausea, vomiting, right upper quadrant pain or tenderness, fever, rash and/or eosinophilia [$>5\%$], and/or total bilirubin ≥ 1.5 xULN or INR >1.5)

The following steps will need to be performed by the investigator:

- The site should immediately contact the subject and require the subject to discontinue IP immediately. The subject should be asked to return to the site within a 48-hour window from awareness of the result.
- A full evaluation of various causes of hepatitis should be conducted (i.e., infectious, alcohol, medications, anatomical).

- An assessment of other concomitant medications and SoC should be made. The investigator should consider whether it is in the best interest of the subject to stop/interrupt concomitant medications and SoC treatment.
- A detailed history including relevant information on alcohol use, recreational drug use, supplement consumption, any herbal remedies, family history, sexual history, travel history, history of contact with a jaundiced subject, surgery, occupational history, blood transfusion, history of liver or allergic disease, and any other potential causes of attributable to a liver insult should be collected.
- A detailed assessment of the subject's clinical condition and repeat laboratory tests for liver function tests (LFTs), including albumin, creatine kinase, total bilirubin (direct and indirect), gamma glutamyl transferase (GGT), INR and alkaline phosphatase should be done.
- Further testing for hepatitis A, B, and C, and for autoimmune hepatitis should be done. Other causes of viral hepatitis (cytomegalovirus or Epstein Barr virus etc) should be excluded. Liver imaging should be considered.
- Referral to a hepatologist or gastroenterologist should be requested.
- All these cases should be reported as SAEs.

Every effort should be made to keep subjects in the study and on treatment. However, the investigator, who may consult the sponsor's medical leader, can consider stopping the study treatment in case of concerns about the subject's safety, serious or severe AEs or worsening of the disease condition, which in the investigator's opinion needs an alternative treatment approach not being covered in the clinical study (e.g., rescue medication). If IP treatment is interrupted due to an SAE, IP could be restarted, as per the investigator's judgement and after consultation with the sponsor medical leader.

When study treatment is discontinued, the subject will be requested to complete the assessments for the ED visit and return for the FU visit. Reason for discontinuation must be documented in the case report form (CRF).

Subjects will be informed prior to clinical study entry that they are allowed to withdraw from the clinical study. At any time and for any reason, a subject's participation in the clinical study may terminate at their request, without prejudice to their future medical care. The subject will be encouraged to share the reason(s) for withdrawal so this can be documented in the source documents, and to complete the ED Visit and follow-up visit for safety assessments, but will not be obliged to do so.

Subjects who withdraw from the clinical study without contact with the site (lost-to-follow-up) should be contacted by the site so that their health status can be assessed and documented in the source documents. The site should make every effort to understand whether the subject is alive, including checking the medical records and contacting general practitioner or relatives, if necessary. All attempts must be documented in the source documents.

The sponsor has the right to terminate the clinical study at any time and for any reason. In this event, the investigator(s) and relevant authorities will be informed of the reason for clinical study termination.

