11.2.1. Action Taken Regarding Investigational Product

The action taken must be described by choosing from:

- Dose not changed: In case no action is taken regarding the IP.
- IP permanently discontinued: In case a subject is permanently discontinued from treatment or withdrawn from the study by the investigator (who may consult the sponsor's medical monitor).
- IP temporarily discontinued: In case the IP is temporarily discontinued by the investigator (who may consult the sponsor's medical monitor).
- Not applicable: Other situations (e.g. in case an AE started after the last IP administration).

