Appendix 9: Algorithm for Elevated Liver Function Tests

| | AST or ALT increase to | | | | |
|------------------------|---|---|---|---|-----------------------------|
| Value Range | $\geq 1.5x$ to $3x$ ULN | $\geq 3x$ to $<5x$ ULN | $\geq 5x$ to $<8x$ ULN | $\geq 3x$ ULN with signs of liver damage ¹ | $\geq 8x$ ULN |
| IP Action | Continue as planned | Reduce or interrupt IP for at least 2 weeks | Interrupt IP for at least 2 weeks Close observation ² | Discontinue IP ² | Discontinue IP ² |
| | | | | | |
| After at least 2 weeks | AST and ALT $<3x$ ULN | AST or ALT $\geq 3x$ ULN | | | |
| | Weekly LFTs for the first 2 weeks (biweekly for the following weeks, or more frequently at investigator's discretion) | Discontinue IP Report SAE and complete liver event page for any of abnormalities listed below ³ : 
 - AST/ALT increase $\geq 8x$ULN - AST/ALT increase $\geq 3x$ULN with signs of liver damage¹ | | | |

¹ Signs of liver damage:

- total bilirubin $\geq 2.0x$ ULN OR international normalized ratio >1.5 , and/or
- symptoms: appearance of fatigue, nausea, vomiting, right upper abdominal quadrant pain or tenderness, fever, rash and/or eosinophilia ($>5\%$)

² Close observation recommendations:

- Monitor 2 to 3 times per week all of the following parameters: ALT, AST, alkaline phosphatase, total bilirubin, eosinophils, INR. If local regulations allow, home visits can be performed if subjects cannot come to the clinical study center.
- Frequency of retesting can be reduced to once a week or less if abnormalities stabilize or the IP has been discontinued; however, monitoring might still be needed more frequently taking into consideration the standard of care and/or changes to this.
- Based upon investigator's discretion gastroenterology or hepatology consultations, additional serology testing, imaging and pathology assessments may be required.
- Re-query history of symptoms, prior and concurrent diseases, concomitant medication and non-prescription medicines, herbal, dietary supplements, alcohol use, recreational drug use, special diets.
- Rule out all of the following: acute viral hepatitis, autoimmune hepatitis, alcoholic hepatitis, non-alcoholic fatty hepatitis, hypoxic/ischemic hepatitis, biliary tract disease, and cholestasis.
- Re-query exposure to environmental chemical agents.

³ The following steps should be followed:

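### Protocol 6.4 gives two total-bilirubin limits (≥2.0× and ≥1.5× ULN) for the same combined liver rule, so a narrow band of results draws conflicting stopping and SAE instructions

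*Protocol*

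**What the plan says.** Protocol 6.4 has two lists on raised liver enzymes.

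- The stopping list has IP discontinued when AST and/or ALT is ≥3× ULN with signs of liver damage. The listed signs are symptoms, eosinophilia >5%, and a laboratory part that ends "2.0 x ULN or international normalized ratio [INR] >1.5", with bilirubin at or above that figure. Short of this rule, interruption or reduction is to be considered at AST/ALT 3 to <5× ULN, and IP is to be interrupted at 5 to <8× ULN.
- The step list repeats the AST/ALT limit, the symptoms, the eosinophilia limit and the INR limit, but its laboratory part ends "1.5 xULN or INR >1.5". Its first step is immediate discontinuation of IP. Its last is "All these cases should be reported as SAEs".

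Two other places restate the rule. Appendix 9, footnote 1, sets bilirubin at ≥2.0× ULN ("ULN OR international normalized ratio >1.5"), and footnote 3 attaches nearly the same steps, including the SAE report. For AST/ALT 3 to <5× ULN without signs of liver damage, the Appendix 9 action is "Reduce or interrupt IP for at least 2 weeks"; at 5 to <8× ULN it is to interrupt for at least 2 weeks. Protocol 11.1.5 lists the combined elevation as an SAE with bilirubin >2× ULN.

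**The concern.** A stopping rule should give one answer for one set of results. Here a site's answer depends on which list it reads, and both lists stand in the same section of the current protocol (version 1.0). No redaction or amendment explains the difference. The step list is not a softer trigger for extra tests, because it requires IP to be stopped and an SAE to be reported.

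Three things can therefore differ between sites for the same result: whether IP is stopped, whether the 24-hour SAE report of Protocol 11.3.2 is made, and whether the subject enters the SAP 6.3.1.8 counts of serious TEAEs and of TEAEs leading to study drug discontinuation.

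**Working it through.** The plan states no figure to reproduce. The check sets the four texts side by side and finds where they disagree.

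**Step 1. Inputs.** All four use AST/ALT ≥3× ULN, INR >1.5, the same symptoms and eosinophilia >5%. They differ in bilirubin.

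| Place | Total bilirubin | Consequence stated there |
|---|---|---|
| Protocol 6.4, stopping list | ≥2.0× ULN | Discontinue IP |
| Protocol 6.4, step list | ≥1.5× ULN | Discontinue IP at once, work-up, SAE |
| Appendix 9, footnotes 1 and 3 | ≥2.0× ULN | Discontinue IP, work-up, SAE |
| Protocol 11.1.5 | >2× ULN | SAE |

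**Step 2. Where the two lists in 6.4 disagree.** The step list must be met and the stopping list not met. Any listed symptom, eosinophilia >5%, INR >1.5 or AST/ALT ≥8× ULN triggers both lists, so all of these must hold:

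- AST/ALT ≥3× and <8× ULN
- bilirubin ≥1.5× and <2.0× ULN
- INR ≤1.5
- no listed symptom and no eosinophilia >5%

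**Step 3. Worked cases** (INR ≤1.5, no listed sign).

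| AST/ALT | Bilirubin | 6.4 stopping list | 6.4 step list | Appendix 9 | 11.1.5 |
|---|---|---|---|---|---|
| 4× | 1.7× | Consider interruption or reduction | Discontinue + SAE | Reduce or interrupt ≥2 weeks | Not listed |
| 7× | 1.7× | Interrupt | Discontinue + SAE | Interrupt ≥2 weeks | Not listed |
| 4× | 2.0× | Discontinue | Discontinue + SAE | Discontinue + SAE | Not listed |
| 4× | 2.1× | Discontinue | Discontinue + SAE | Discontinue + SAE | SAE |
| 8× | any | Discontinue | Discontinue + SAE | Discontinue + SAE | SAE |

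Reduction is named in the text but is hardly a real option. There is one dose level (Protocol 5.1), the whole solution must be drunk (7.2), and the action-taken list in 11.2.1 has no entry for it. The practical contrast is interrupting, or considering it, against discontinuing.

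**Step 4. Extent.** Cross four AST/ALT bands (<3, 3 to <5, 5 to <8, ≥8× ULN) with four bilirubin bands (<1.5, 1.5 to <2.0, exactly 2.0, >2.0× ULN): 4 × 4 = 16 cells. The initial stopping decision conflicts in 2 cells, AST/ALT 3 to <5× and 5 to <8× at bilirubin 1.5 to <2.0×. At exactly 2.0×, the same two AST/ALT bands differ only in that 11.1.5 does not list them; the 6.4 step list and Appendix 9 already require the SAE. The cells are a way of enumerating the rules and say nothing about how often each occurs.

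**Step 5. Effect of one subject at planned numbers.** GLPG3970: 1/20 = 5%. Placebo: 1/10 = 10%.

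**The case against.** The best defence is that a site can follow the stricter list without breaching anything. Section 6.4 lets the investigator stop treatment on safety grounds, and 11.1.2 allows an event to be called serious on medical judgement. The list in 11.1.5 is not stated to be exclusive. An internal committee reviews unblinded safety data (Protocol 10.1). Protocol 5.5 sends laboratory alerts at Grade 3 and above to the investigator and sponsor. If those alerts use the SAP Appendix I grades (an assumption), AST/ALT above 5× ULN is Grade 3 and would reach the sponsor anyway.

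This limits the harm, but being allowed to follow the stricter list does not make the two lists agree. Section 6.4 also asks for every effort to keep subjects on treatment and refers sites to Appendix 9, which gives the more lenient answer. On the same alert assumption, AST/ALT between 3× and 5× ULN with bilirubin 1.5 to <2.0× ULN does not reach Grade 3, so no alert would follow.

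A reader might infer more than the documents support:

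- **That 6.4 leaves discontinuation open to restart.** Section 6.4 sends subjects whose treatment is discontinued to the early-discontinuation and follow-up visits. Its restart sentence concerns interruption only: "If IP treatment is interrupted due to an SAE, IP could be restarted".
- **That the Appendix 9 recheck after 2 weeks is missing from 6.4.** The liver entry in 6.4 refers to Appendix 9, which states it.
- **That the conflict stems from admitting subjects with Gilbert's disease.** How their raised bilirubin is handled is a question under any single limit.
- **That the event would go unrecorded.** Under 11.1.5, an abnormality that leads to interruption is recorded as an AE or SAE if it meets the definition.

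**Conclusion.** Wrong as written. Section 6.4 has two bilirubin limits for one rule, and with Appendix 9 and 11.1.5 there are three cut-offs in four places (≥1.5×, ≥2.0× and >2× ULN). The conflict on stopping is confined to the band in Step 2. The documents give no frequency for such results, and few cases are likely. Safety is summarised descriptively with no formal testing (SAP 6.3), so the effect is on subject handling and on small counts.

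The 1.5× figure looks like the outlier, because the stopping list and Appendix 9 use ≥2.0× and 11.1.5 is close to it. That is an inference; the documents do not say which limit was intended.

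It would be too strong to infer that the efficacy result or the liver evaluation is compromised. The sample size and primary analysis method do not depend on this rule. SAP 6.3.2.8 tabulates AST or ALT >3× ULN with same-day bilirubin at both >1.5× and >2× ULN, so the planned liver tables show these results whichever list a site followed. The point should be corrected because it concerns a safety stopping rule and costs almost nothing to put right.

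**What to change.** Use one bilirubin limit with one inequality sign in both 6.4 lists, Appendix 9 and 11.1.5.

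- **Default, ≥2.0× ULN.** This matches the 6.4 stopping list and Appendix 9. It takes two edits: change 1.5 to 2.0 in the 6.4 step list, and change > to ≥ in 11.1.5.
- **Alternative, ≥1.5× ULN.** If the medical team prefers the more cautious limit, change the 6.4 stopping list, 11.1.5 and Appendix 9 footnote 1 instead, which is three edits.

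The cost is protocol amendment wording only. No visits, procedures or subjects are added, and the SAP liver tables need no change.
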